At least two different clinicians will evaluate the device for each patient and for each needle for that patient (test and control) to minimize the bias associated with the same clinician evaluating all of the sessions for a given subject.

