9.1.3 Test Dialysis Sessions

The assessment of the ability to successfully complete the session will be determined by the clinician and recorded on the Therapy Assessment Case Report Form (CRF). The actual treatment time will also be recorded. Adverse events will be recorded on an Adverse Event Case Report Form. Photos of the cannulation may be taken.

Additional performance measures include the following:

- Machine alarm rate (blood alarms only) during hemodialysis therapy, including false alarms and relationship of alarm to venous needle
- Changes to blood flow rate setting during therapy sessions and relationship to venous needle
- Venous, transmembrane, and/or arterial pressure measurements
- Patient survey including ratings for venous needle comfort and feelings of safety (V Needle only)
- Clinician survey, evaluating the following items:
 - use of the device according to the instructions for use (IFU)
 - ability to properly cannulate
 - ability to objectively see flashback
 - confirmation that the footplate is fully depressed (V Needle only)
 - feelings regarding patient risk (V Needle only)
- Achieved treatment time
- Achieved blood flow rate
- Ability to cannulate fistula
- Episodes of partial or complete needle dislodgment

In the event that the venous needle becomes 1) completely dislodged, or 2) partially dislodged and the venous pressure increases by more than 40 mm Hg (above last recorded venous pressure measurement) indicating some disruption of the fluid flow, the event should be recorded on the therapy assessment and AE CRFs and appropriate laboratory tests (including CBC, plasma hemoglobin concentration, serum electrolytes) shall be obtained.

Patients shall be monitored for symptoms of hemolysis; if hemolysis is suspected, an AE form should be completed and appropriate laboratory tests (including CBC, plasma hemoglobin concentration, serum electrolytes) shall be obtained.

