10.3 Statistical Analyses

10.3.1 Performance Endpoint Analysis

Although not a randomized study, each subject dialysis session will be performed using either the test needle or a control needle. The sites are instructed to perform 3 control sessions first and then 6 test sessions per enrolled subject, and in the case that a site deviates from this order, performance measure will be analyzed based on the needle used. Assuming there will be a 20% rate of attrition/drop-out, the remaining 18 subjects would contribute 108 test and 54 control sessions. Data will be pooled by session type (test vs. control) from all sites (no by-site analyses are planned).

The primary performance analysis will test the non-inferiority hypothesis as a difference of proportions between the test and control groups using a one-sided Farrington-Manning Score Test at a significance level of $\alpha=0.025$.

Additionally, the primary performance measure will be analyzed on the subject-level (utilizing a non-inferiority margin of 0.05) by testing the difference in mean success rates per subject across treatment groups using a one-sided paired t-test at a significance level of $\alpha=0.025$.

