10.3.3 Usability and Additional Measures

The results from the clinician and patient surveys (formatted on ordinal scaling) will each be summarized using the 5-point Likert scoring system (e.g., 5=strongly agree, 4=agree, 3=neither agree or disagree, 2=disagree, 1=strongly disagree) to represent user responses on a symmetric range, with overall item scores to represent usability measures. The usability of the V Needle will be assessed from the clinician and patient survey scores submitted for the needle device used at the end of each session. This will be done using a Mann-Whitney-Wilcoxon (MWW) test, which will assess differences in mean ranks of clinician/patient survey scores given to the V Needle and control devices, as applicable.

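### The clinician survey comparison uses an unpaired rank-sum test on repeated session scores, so its p-values are not valid in general, in a direction the documents do not fix

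*Combined protocol and SAP*

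**What the plan says.** Section 10.3.3 (Usability and Additional Measures) bases usability on "survey scores submitted for the needle device used at the end of each session", scored on a 5-point scale. The comparison is to be made "using a Mann-Whitney-Wilcoxon (MWW) test, which will assess differences in mean ranks of clinician/patient survey scores given to the V Needle and control devices". A closing qualifier, as applicable, is attached without saying which items it covers. No sidedness, pairing, averaging, subject effect or clinician effect is given.

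The scores are repeated by design. Under 10.3.1 sites are to "perform 3 control sessions first and then 6 test sessions per enrolled subject", and "the remaining 18 subjects would contribute 108 test and 54 control sessions". Section 5.1 adds: "At least two different clinicians will evaluate the device for each patient and for each needle for that patient (test and control").

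Sections 9.1.2 and 9.1.3 show which items can be compared:

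- **Clinician items at both control and test sessions:** use according to the instructions, ability to cannulate, and visible flashback.
- **Clinician items for the V Needle only:** footplate confirmation and feelings about patient risk.
- **Patient survey:** "Patient survey including ratings for venous needle comfort and feelings of safety (V Needle only"). Table 1 in 1.23 schedules it at test sessions only.

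Section 10.4.1 puts descriptive results at session level and names one within-subject exception, the additional analysis of the primary measure.

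**The concern.** The design makes each subject their own control, and 10.3.1 uses a paired t-test for the additional primary analysis. The survey comparison discards that structure. A rank-sum test takes its variance from independent observations, but nine sessions on one subject share that subject's access, and sessions rated by one clinician share that clinician's scoring habits. The variance is then misstated.

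Usability is one of the three stated objectives (1.4, section 4), and this is the only inferential analysis of it in the plan. A reader of the report would have no basis for treating the p-value as either cautious or optimistic. The wording also names patient scores on both devices, although no patient control scores will exist.

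**Working it through.** The plan states no size, power or effect for the survey test, so there is no figure to reproduce. The 87 test sessions in 10.1.1 belong to the primary endpoint and do not bear on this point.

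**Inputs from the documents.** 18 subjects; 18 × 6 = 108 test scores and 18 × 3 = 54 control scores; a 5-point scale; alpha 0.05 if two-sided (10.4.1). A two-sided test is assumed, because 10.3.3 does not say.

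**Assumptions, because the documents are silent.** ρ is the share of score variance between subjects (or clinicians). τ is the variance of the needle effect between them. The null is no average needle effect. Total variance is set to 1.

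**Step 1: direction, by approximation with means.**

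- Variance of the test-minus-control difference if all scores are independent: 1/108 + 1/54 = 3/108 = 1/36.
- True variance with a shared subject effect only: the subject effect cancels, because every subject contributes in the same 6:3 ratio. This leaves (1 − ρ)/36.
- Effective critical value: 1.96/√(1 − ρ). At ρ = 0.3 this is 1.96/0.837 = 2.34, a two-sided size of about 1.9%. At ρ = 0.5 it is 1.96/0.707 = 2.77, about 0.6%.
- If the needle effect varies between subjects, add τ/18 = 2τ/36. The true variance is then [(1 − ρ) + 2τ]/36. It passes 1/36 at roughly τ = ρ/2, ignoring the extra spread that τ adds to the scores. Below that the test is too cautious, and above it too liberal.

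**Step 2: simulation with subject clustering.** Latent normal scores are cut into 5 categories, with 18 subjects, 2,000 runs per setting and no average needle effect. The Monte Carlo standard error at 5% is √(0.05 × 0.95/2000) = 0.5 points. The table gives the true size of the nominal 5% rank-sum test.

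| ρ | τ = 0 | τ = 0.1 | τ = 0.3 | τ = 0.5 |
|---|---|---|---|---|
| 0 | 5.0% | 5.3% | 10.4% | 13.0% |
| 0.3 | 2.2% | 4.4% | 8.4% | 10.6% |
| 0.5 | 1.2% | 2.6% | 5.8% | 9.2% |
| 0.7 | 0.2% | 1.4% | 4.6% | 7.7% |

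Separate simulations gave 2.2% to 2.7% at ρ = 0.3 and 0.9% to 1.0% at ρ = 0.5 with τ = 0, and 6.8% to 7.0% at ρ = 0.3 with τ = 0.3. A signed-rank test on subject mean differences stayed between 4.2% and 5.6% in all 18-subject settings.

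**Step 3: power for a latent shift of 0.4, τ = 0.** Rank-sum against signed-rank: 58% against 51% at ρ = 0, 57% against 60% at ρ = 0.3, and 61% against 74% at ρ = 0.5. Pairing gains once ρ is appreciable and loses a little if it is zero.

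**Step 4: clinician clustering.** The 108 and 54 scores are clustered by 4, 8 or 12 clinicians, with ρ from 0.1 to 0.5 (all assumed). Size of the rank-sum test:

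- clinicians evenly spread over the needles, τ = 0: 4.5% to 6.8%;
- evenly spread, τ = 0.3: about 13% to 30%;
- unevenly spread, τ = 0: about 10% to 40%.

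**Step 5: does the paired test repair Step 4?** No. With 6 evenly spread clinicians, ρ = 0.3 and clinician-by-needle variance 0.3 (1,000 runs), size was 20.7% for the rank-sum test and 22.4% for the signed-rank test. With uneven spread and no such variance it was 14.5% and 13.0%. With 10 evenly spread clinicians, ρ = 0.3 and needle effects varying between clinicians, it was 13.0% and 17.7%.

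**The case against.** The strongest reply has four parts.

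- **The qualifier.** The phrase as applicable can fairly be read as confining the test to items that have control scores. A reader might infer that the plan will test patient scores against a control. The documents do not support that, since patients never rate a control needle. What remains is that 10.3.3 does not list the items compared.
- **The raters.** A reader might infer that a few clinicians rate both needles. Section 5.1 requires at least two clinicians per patient and needle, and gives neither their number nor their overlap between needles. The larger figures in Step 4 are possibilities under assumption. If clinicians are evenly spread and do not differ in needle effect, size stays near nominal.
- **The direction.** A reader might infer that false usability claims become more likely. With a shared subject effect only, the test errs towards caution. This limits the alarm but does not validate the test.
- **The stakes.** Section 1.18 plans no powered secondary performance measures, the surveys are listed as additional measures, and no success criterion rests on this p-value.

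All four stand as limits on the point. None supplies the missing allowance for subject or clinician, and nothing elsewhere in the plan does.

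**Conclusion.** The test is wrong as written for the three clinician items scored on both needles. An independent-samples test is applied to repeated session scores, so its p-values are not valid in general. Under assumed subject correlations of 0.3 to 0.5 with a shared subject effect only, the true size is about 1% to 3% and power is lost. With needle-effect variance 0.3 between subjects and correlation 0.3, it is about 7% to 8%. If clinicians differ in needle effect or are unevenly spread, it can be 10% or more. Every correlation and variance here is an assumption, and the documents do not settle the direction.

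A reader might go further and conclude that the p-values are known to be too small, or that the trial's main conclusion is at risk. Neither follows: the sign of the error is undetermined, and the primary performance test is a separate analysis that this point does not touch. For patient scores the defect is one of wording, since no control comparison is possible.

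**What to change.** In 10.3.3:

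1. Name the three shared clinician items (use according to the instructions, cannulation, flashback) as the only ones compared between needles.
2. Analyse each with an ordinal mixed model, with needle as a fixed effect and subject and clinician effects, including clinician-by-needle where it can be estimated.
3. Give a Wilcoxon signed-rank test on subject-level mean differences as the simple paired analysis, and state that it handles clustering by subject but not by clinician.
4. State whether the tests are two-sided.
5. Report the patient survey and the V Needle-only clinician items descriptively, and replace the clinician/patient wording accordingly.

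This changes wording only and needs no added subjects or visits. The clinician survey is already planned at both control and test sessions, but the rater's identity must be recorded with each score. The cost is slightly more analysis work, and the model may be hard to fit with few clinicians.

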10.3.4 Alarm categories and definitions

The following definitions are used for dialysis machine alarms:

True Alarm: Alarm was appropriate because clinician action was required beyond resetting the alarm (e.g., venous needle dislodgement, significant needle movement, infiltration, tape failure), and/or V Needle footplate opened appropriately.

False Alarm: No clinician action was required beyond resetting the alarm, and/or V Needle footplate opened inappropriately.

The following definitions will be used for the footplate opening:

Appropriate footplate opening: Footplate opening due to a VND or infiltration and/or needle movement, tape failure, or other condition that can potentially lead to a VND or infiltration.

Inappropriate footplate opening: Footplate opening that is not due to a VND or infiltration and/or needle movement, tape failure, or other condition that can potentially lead to a VND or infiltration

10.4 Other Statistical Considerations

10.4.1 General/Summary Metrics

Simple descriptive statistics will be displayed for all relevant variables collected under the study, and be presented on the session-level (between-subject), with the exception of the additional analysis of the primary performance measure which will be done on the individual-level (within-subject).

Continuous variables will display number of observations/counts measured, mean, standard deviation, median, min/max, Q1/Q3, and 95% confidence intervals where appropriate; categorical variables will display frequency counts and percentages.

These variables will include but are not limited to the following:

- Subject demographics (including age, gender, weight, height, etc.)
- Medical history characteristics (including concomitant medication, duration in which subject was diagnosed with renal disease, any concurrent ailments, etc.)

Unless otherwise specified, all p-values will be considered significant at $\alpha=0.05$ if tests are two-sided and $\alpha=0.025$ if tests are one-sided.

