1.23 SCHEDULE OF ACTIVITIES (SOA)

Table 1: Schedule of Activities

	Enrollment Visit	Control Dialysis Sessions (Visit 1-3)	Test Dialysis Sessions (Visit 4-9)	Final Study Visit (7-10 days after Visit 9)
Informed Consent	X			
Inclusion/Exclusion	X			
Demographics	X			
Medical History Form	X			
Vital Signs	X			
Adverse Event Form	X	X	X	X
Therapy Assessment Form, including the following: 
• Treatment success/failure• Blood alarms• Flow rates• Prescribed treatment time• Achieved treatment time• Prescribed blood flow rate• Achieved blood flow rate• Ability to cannulate fistula		X	X	
Patient Survey			X	
Clinician Survey		X	X	

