3.3 Risk/Benefit Assessment

3.3.1 Known Potential Risks

Risks related to the study and/or device are expected to be the same as those risks for patients undergoing hemodialysis. Due to the design of the V Needle, very slight increases in certain risks are potentially possible but are not expected.

The potential risks specifically associated with the V Needle are as follows:

- Improper needle function, leading to machine false alarms or changes to dialysis blood flow rate or pressure
- Difficulty inserting the needle into the veins (cannulation)
- Slightly increased risk of blood loss and/or air embolism

The risks associated with all AV fistula sets are as follows:

- Air in the tubing/blood vessels, which could result in blockage and reduced blood flow in that vessel or other vessels in the body
- Allergic responses to the device materials, such as swelling, itchiness, or inflammation of the skin
- Small particles released into the blood vessels, which could result in blockage and reduced blood flow in that vessel or other vessels in the body
- Improper function of the device, leading to delay in therapy
- Infection
- Breakdown of blood cells due to unstable blood flow (hemolysis), which can lead to fatigue, dizziness, and headaches
- Blood loss
- Blood leaks into surrounding tissue, leading to swelling and/or pain (infiltration, when the needle tip is placed into the body but not directly into the blood vessel)
- Injury from sharp needle

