9.1.2 Control Dialysis Sessions

The assessment of the ability to successfully complete the session will be determined by the clinician and recorded on the Therapy Assessment Case Report Form (CRF). The actual treatment time will also be recorded. Adverse events will be recorded on an Adverse Event Case Report Form. Photos of the cannulation may be taken.

Additional performance measures include the following:

- Machine alarm rate (blood alarms only) during hemodialysis therapy, including false alarms and relationship of alarm to venous needle
- Changes to blood flow rate setting during therapy sessions and relationship to venous needle
- Venous, transmembrane, and/or arterial pressure measurements
- Clinician survey, evaluating the following items:
 - use of the device according to the instructions for use (IFU)
 - ability to properly cannulate
 - ability to objectively see flashback
- Achieved treatment time
- Achieved blood flow rate
- Ability to cannulate fistula
- Episodes of partial or complete needle dislodgment

In the event that the venous needle becomes 1) completely dislodged, or 2) partially dislodged and the venous pressure increases by more than 40 mm Hg indicating some disruption of the fluid flow, the event should be recorded on the therapy assessment and AE CRFs and appropriate laboratory tests (including CBC, plasma hemoglobin concentration, serum electrolytes) shall be obtained.

Patients shall be monitored for symptoms of hemolysis; if hemolysis is suspected, an AE form should be completed and appropriate laboratory tests (including CBC, plasma hemoglobin concentration, serum electrolytes) shall be obtained.

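### Session-level 95% confidence intervals on device means would treat each subject's repeated sessions as independent and come out too narrow

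*Combined protocol and SAP*

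**What the plan says.** Section 10.4.1 (General/Summary Metrics) sets the rule for all descriptive output: "Simple descriptive statistics will be displayed for all relevant variables collected under the study, and be presented on the session-level (between-subject"). The one exception it names is the additional analysis of the primary performance measure, done within subject. For continuous variables it lists the usual summaries and "95% confidence intervals where appropriate". It gives no method for those intervals and mentions no allowance for repeated sessions.

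The repetition is built into the design. Section 5.1 has each subject undergo three control sessions and then six with the V Needle, and section 10.3.1 states that "the remaining 18 subjects would contribute 108 test and 54 control sessions".

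Several continuous variables are collected at every one of these sessions. Sections 9.1.2 and 9.1.3 list "Venous, transmembrane, and/or arterial pressure measurements", achieved treatment time and achieved blood flow rate. They bear on a risk the sponsor names for this device in section 3.3.1: "Improper needle function, leading to machine false alarms or changes to dialysis blood flow rate or pressure".

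**The concern.** Readings from one subject share an access, a prescription and a circulation, so they are likely to be more alike than readings from different subjects. The usual interval for a mean divides the variance by the number of readings, which is right only if the readings are independent. Applied to 108 V Needle sessions from 18 subjects, it claims more information than the data hold.

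What is at stake is how the supporting performance tables are read. A mean venous pressure or achieved flow for the V Needle would carry an interval that looks firmer than it is. The distortion is larger for the V Needle (six sessions per subject) than for the control (three), so the new device's results would be the more overstated in precision.

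**Working it through.** **Inputs from the documents.** Sessions per subject: m = 6 (V Needle) and m = 3 (control), section 5.1. Planned subjects: k = 18, sections 10.1.1 and 10.3.1. The plan's session counts reproduce: 18 × 6 = 108 and 18 × 3 = 54.

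**Assumed input.** The ICC of a reading between sessions of one subject on one device. The documents give none, so 0.3, 0.5 and 0.8 are shown.

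**Step 1: a device mean.** The true variance of the mean is the independent-sessions variance times the design effect, DE = 1 + (m − 1) × ICC. The true standard error is √DE times the naive one, and a nominal 95% interval covers approximately 2Φ(1.96/√DE) − 1.

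| m | ICC | DE | √DE | Coverage | Effective sessions (18m/DE) |
|---|---|---|---|---|---|
| 6 | 0.3 | 2.5 | 1.58 | 78.5% | 43.2 of 108 |
| 6 | 0.5 | 3.5 | 1.87 | 70.5% | 30.9 of 108 |
| 6 | 0.8 | 5.0 | 2.24 | 61.9% | 21.6 of 108 |
| 3 | 0.3 | 1.6 | 1.26 | 87.9% | 33.8 of 54 |
| 3 | 0.5 | 2.0 | 1.41 | 83.4% | 27.0 of 54 |
| 3 | 0.8 | 2.6 | 1.61 | 77.6% | 20.8 of 54 |

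Coverage depends on m and the ICC, not on k, so it is the same anywhere in the planned range of 15 to 20 subjects. A simulation of 20,000 trials (18 subjects, six sessions each) gave 78.5% at ICC 0.3 and 70.1% at 0.5 for the naive interval. A t interval on the 18 subject means gave 95.0% at both.

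**Step 2: width of a correct interval.** On the standard-error scale, the V Needle interval widens by √DE: 1.58, 1.87 and 2.24 times. A t interval on subject means also swaps the quantile for 107 degrees of freedom (1.982) for that with 17 (2.110), a factor of 1.064. The full widening is then 1.68, 1.99 and 2.38 times.

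**Step 3: a V Needle minus control difference.** The plan commits to no such interval for these variables, but one could be added under the same wording. Set the total variance of a reading to 1. Let B be the share due to subject-by-needle variation, that is, subjects differing in how their readings shift between devices. An independent-sample calculation gives variance 1/108 + 1/54 = 1/36. The true variance is

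[(1 − ICC)(1/6 + 1/3) + 2B]/18 = (1 − ICC)/36 + 4B/36.

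The two are equal when B = ICC/4. Below that the independent-sample interval is too wide; above it, too narrow. With B = 0, the naive standard error is 1/√(1 − ICC) = 1.20, 1.41 and 2.24 times the true one at the three ICCs. At ICC 0.5 and B = 0.25, the ratio is √(1/(0.5 + 1.0)) = 0.82. Per-subject paired differences are valid in either case.

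**The case against.** The strongest reply is that the plan does not commit to the intervals being criticised. Section 10.4.1 offers them only where appropriate, names no method and does not mention pressure or flow. The variables it gives as examples are demographics and medical history, which are recorded once per subject. A sensible analyst could judge a naive session-level interval inappropriate and leave it out. The measures are also unpowered and descriptive.

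This limits the weight of the point but does not remove it. The example list is expressly open-ended, the rule covers every relevant variable, and the session level is stated outright with a single exception. An analyst following the text would build any interval on sessions.

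A reader might go further and infer that venous pressure is never read together with pump flow, so that added needle resistance could be hidden when staff turn the pump down. The documents do not support that:

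- The form is not in the documents. The schedule introduces its contents with "Therapy Assessment Form, including the following", so the absence of a pressure item there proves nothing.
- The trigger in section 9.1.2, "partially dislodged and the venous pressure increases by more than 40 mm Hg indicating some disruption of the fluid flow", presupposes an earlier reading, and section 9.1.3 refers to the last recorded one.
- Section 9.1.3 also lists "Changes to blood flow rate setting during therapy sessions and relationship to venous needle", so needle-related turn-downs would be on record.
- A table of pressure during delivered therapy is valid as that, and the documents give no turn-down rate, resistance or pressure variability from which to size a masking effect.

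A reader might also infer that an independent-sample interval for the device difference is always too wide. Step 3 shows that this depends on subject-by-needle variation, about which the documents say nothing.

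**Conclusion.** The point holds for 95% intervals on device means of variables measured at more than one session per subject. Built as section 10.4.1 reads, a nominal 95% interval would cover roughly 62% to 79% for the V Needle and 78% to 88% for the control, over an assumed ICC of 0.3 to 0.8. The direction needs only a positive ICC. The size rests on that assumed range, on equal correlation between a subject's sessions, and on all planned sessions being completed.

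This is a minor improvement to the descriptive reporting. It does not bear on the primary performance test, the 87-session requirement, the primary safety measure or the stopping rule. It gives no ground for adding a new pressure-and-flow measurement.

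**What to change.** Add to section 10.4.1 that:

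- any 95% confidence interval for a variable measured at more than one session per subject is based on subjects, either as a t interval on subject means or with a cluster-robust standard error;
- any V Needle minus control interval uses per-subject paired differences.

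Session-level counts, means, medians and ranges can stay as planned. The approach is already in the plan, since section 10.3.1 uses a subject-level paired t-test for the additional primary analysis.

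The cost is wider per-device intervals, as sized in Step 2, which is the honest width. No data, visits or form changes are needed. Because the analysis text sits in the protocol, the wording change would go through the IRB review that section 2 requires for any amendment.

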3.1 Study Rationale

In patients undergoing hemodialysis for the treatment of end-stage renal disease, Venous Needle Dislodgement (VND) is a rare, but potentially fatal situation in which the needle delivering a patient's blood back to the body after filtration by a dialysis machine becomes inadvertently disconnected from the patient. Hemotek Medical Inc. has developed the V Needle, a venous needle return that is designed to reduce patient risk from exsanguination-related injury or death. This clinical study will serve as a confirmatory study to gain FDA marketing clearance of the Hemotek V Needle system in the clinical setting. During this study, we will determine the ability of the V Needle to successfully deliver appropriate hemodialysis therapy per the facility's guidelines. It will also be used to determine if the V Needle triggers false blood alarms under normal operating conditions. This study will also be used to demonstrate the V Needle meets effective usability criteria. Rates of adverse events and ability to complete the hemodialysis session will be compared to the rates recorded using commercially available devices during the hemodialysis sessions prior to the use of the Hemotek V Needle.

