4.4 ADDITIONAL PERFORMANCE MEASURES

- Machine alarm rate (blood alarms only) during hemodialysis therapy, including false alarms and relationship of alarm to venous needle
- Changes to blood flow rate setting during therapy sessions and relationship to venous needle
- Venous, transmembrane, and/or arterial pressure measurements
- Patient survey including ratings for venous needle comfort and feelings of safety (V Needle only)
- Clinician survey, evaluating the following items:
 - use of the device according to the instructions for use (IFU)
 - ability to properly cannulate
 - ability to objectively see flashback
 - confirmation that the footplate is fully depressed (V Needle only)
 - feelings regarding patient risk (V Needle only)
- Achieved treatment time
- Achieved blood flow rate
- Ability to cannulate fistula

- Episodes of partial or complete needle dislodgment

5 Study Design

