6.1 Inclusion Criteria

In order to be eligible to participate in this study, an individual must meet all of the following criteria:

1. Subjects with end-stage renal disease receiving chronic hemodialysis in a clinical setting.
2. Subjects must be able to receive hemodialysis with the Hemotek 15-gauge, 1 inch length V Needle, with 12 inch tubing.
3. Age greater than 18 years old at screening.
4. Vascular access via a mature arteriovenous (AV) fistula or graft in the arm and determined to be adequate for a chronic hemodialysis therapy.
5. AV fistula has already been demonstrated to adequately permit one or more hemodialysis sessions.
6. Subject prescribed blood flow rates between 200 ml/min and 450 ml/min
7. In women with child-bearing potential, negative urine or serum pregnancy test at Screening.
8. Subject able to communicate effectively with investigative staff, competent and willing to give written informed consent, and able to comply with entire study procedures.
9. Hemoglobin ≥ 9 g/dL (consistent with KDOQI guidelines)

10. Normal platelet count ($\geq 150,000 /mm^3$)
11. International Normalized Ratio (INR) ≤ 1.5

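### Achieved blood flow and treatment time are summarised only across sessions; a within-subject V Needle minus control difference would use the own-control design at almost no cost

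*Combined protocol and SAP*

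**What the plan says.** One stated purpose of the study is to "determine the ability of the V Needle to successfully deliver appropriate hemodialysis therapy" (section 3.1). Section 3.3.1 lists, as a risk specific to the V Needle, "Improper needle function, leading to machine false alarms or changes to dialysis blood flow rate or pressure".

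The additional performance measures in sections 1.19 and 4.4 include "Achieved blood flow rate" and achieved treatment time. Neither is defined relative to the prescription. The Therapy Assessment Form in Table 1 (section 1.23) also records "Prescribed treatment time" and "Prescribed blood flow rate" at both control and test sessions. Eligibility (section 6.1) requires "Subject prescribed blood flow rates between 200 ml/min and 450 ml/min".

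Section 10.4.1 governs the descriptive summaries. They are "presented on the session-level (between-subject), with the exception of the additional analysis of the primary performance measure". On content: "Continuous variables will display number of observations/counts measured, mean, standard deviation, median, min/max, Q1/Q3, and 95% confidence intervals where appropriate". The section does not name achieved flow or time, but it covers all relevant collected variables and its list of examples is open-ended. Section 10.3.1 pools sessions by needle. Section 10.3.3, despite a title that includes additional measures, deals only with the surveys. Section 10.4.2 uses available data without imputation. No section plans a paired or prescription-relative summary of flow or time.

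**The concern.** The primary success question (section 10.1.2) asks only whether a session was incomplete because of vascular access. A session finished at reduced flow counts as a success. The quantitative evidence on delivered therapy therefore comes mainly from achieved flow and achieved time.

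The design gives each subject three control and six V Needle sessions, so the natural comparison is within subject. A summary across pooled sessions instead carries the spread between patients. The widest eligible prescription is 2.25 times the narrowest (450/200). Two things follow. A modest fall in delivered flow may be hard to see against that spread. If some subjects contribute fewer V Needle sessions than others, the pooled V Needle mean may also move with no device effect. Such imbalance is plausible: section 6.3 treats subjects who do not complete the control sessions as screen failures, so in counted subjects the losses fall on the V Needle side, and section 10.1.1 allows for 20% attrition or missed sessions.

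**Working it through.** **The plan's own figure.** The documents give no figure for achieved flow or time. The nearest stated figure is the 87 V Needle sessions for the primary endpoint. It reproduces: the exact power of the one-sided Farrington-Manning test (98% in both groups, margin 0.08, one-sided 0.025) is 85.5% with 87 test and 44 control sessions. Nothing below alters it.

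**Inputs from the documents.** 18 subjects, 54 control and 108 test sessions (10.3.1); 87 test sessions required (10.1.1); 15 subjects with 9 treatments each expected (5.3), which is 15 × 6 = 90 test sessions; eligible flow 200 to 450 ml/min (6.1).

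**Assumptions not in the documents.** Between-subject SD of flow, s_b: 40 to 72 ml/min, where 72.2 = 250/√12 is the SD if prescriptions were uniform over the eligible range. Within-subject session SD, s_w: 10 to 25 ml/min. The needle effect is the same in every subject; if it varies, the within-subject interval widens.

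**Precision with complete data (3 control, 6 test sessions each)**

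- Session-level SE = √(s_b² + s_w²) × √(1/108 + 1/54) = √(s_b² + s_w²)/6; half-width = 1.96 × SE.
- Within-subject SE = s_w × √(1/3 + 1/6)/√18 = s_w/6; half-width = 2.11 × SE (t, 17 df).

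| s_b | s_w | Session-level half-width (ml/min) | Within-subject half-width (ml/min) | Ratio |
|---|---|---|---|---|
| 72.2 | 10 | 23.8 | 3.5 | 6.8 |
| 72.2 | 25 | 24.9 | 8.8 | 2.8 |
| 40 | 10 | 13.5 | 3.5 | 3.8 |
| 40 | 25 | 15.4 | 8.8 | 1.8 |

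With complete data the two point estimates agree, because every subject has the same 3:6 weighting. Only the interval differs. In 4,000 simulated trials with uniform prescriptions, s_w = 15 and a true shortfall of 20 ml/min, both estimates averaged about −20. The session-level interval excluded zero in 17% of trials and the within-subject interval in 100%.

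**Patient mix with unequal V Needle counts, no device effect.** Assume prescriptions evenly spaced over 200 to 450 (mean 325). Shift = −(sum of deviations from 325 over the lost sessions)/(sessions left).

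- 15 subjects, 3 sessions lost, all from the lowest-flow subject (deviation −125): 3 × 125/87 = +4.3 ml/min.
- 18 subjects, 21 sessions lost. The spacing is 250/17 = 14.7, so the four lowest deviations are −125, −110.3, −95.6 and −80.9. Losing all six sessions from the first three subjects and three from the fourth gives (6 × 330.9 + 3 × 80.9)/87 = +25.6 ml/min. Losing the highest-flow sessions instead gives −25.6.
- The same 21 sessions missed individually at random: the shift averages zero with SD about 3.6 ml/min. If whole subjects are lost at random, the SD is about 8 ml/min.

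**Treatment time.** The documents give no range of prescribed times, only a typical session of around three hours (section 1.12). No comparable figure can be given.

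**The case against.** The strongest reply is that the plan describes these summaries only as descriptive. It specifies no V Needle minus control contrast for flow or time, so the session-level interval in the table is one a reader might construct, not one the plan promises. This stands, and it is why the point concerns an omitted better summary and not an erroneous test.

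A reader might infer that the prescribed values go unused. The documents do not support that. Section 10.4.1 covers all relevant collected variables, so prescribed flow and time may well be tabulated beside the achieved values, and a shift in patient mix would then show in both rows. What is absent is any planned summary that links the two.

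A reader might also infer that a V Needle shortfall would go unnoticed. That is too strong. Sections 4.4, 9.1.2 and 9.1.3 record changes made to the flow setting and whether the venous needle was the cause, under both needles, together with line pressures and blood alarms. This is a real safeguard, though a partial one: it rests on unblinded attribution (section 7.3) and does not measure the shortfall against prescription.

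Finally, the large mix shift is a constructed worst case. Nothing in the documents links missed sessions to prescribed flow, the shift vanishes with complete data, and eligibility limits are not a distribution of prescriptions. All of this stands. The loss of precision remains even with complete data.

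**Conclusion.** The point holds as an optional improvement. The plan summarises achieved flow and time across sessions only, and the design supports a more precise and mix-free summary from data already collected. Under the assumed SDs, the session-level interval for the flow difference is about 1.8 to 6.8 times wider than the within-subject one. The mix shift ranges from zero (complete data), through at most about 4 ml/min (15 subjects, 3 sessions lost), to about 26 ml/min in either direction (18 subjects, 21 lost, worst case). Every ml/min figure depends on an assumed spread of prescriptions, and the interval widths also on an assumed session SD. No size is claimed for treatment time.

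A reader might extend this to the primary conclusion. The documents do not support that: these are unpowered additional measures, and the primary Farrington-Manning test, its subject-level paired analysis and the 87-session requirement do not depend on them.

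**What to change.** In sections 10.3 and 10.4.1, add for achieved blood flow and achieved treatment time the within-subject V Needle minus control mean difference with a 95% CI. The subject is the unit, and each subject with at least one V Needle session contributes one difference. Report it both as achieved values and as a percentage of prescribed.

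Show the prescribed values by needle in the same table. The percentage alone would hide a prescription that was lowered during the V Needle phase; the achieved values and the prescribed row make such a change visible. A product of the flow and time percentages is not needed, as it would add a further measure that the plan does not define.

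Keep the session-level table as planned. The cost is a few lines of SAP text and one extra descriptive table, with no new data, visits or subjects.
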